11.5 Study Monitoring

In satisfaction of common regulatory requirements and *current good clinical practice* (cGCP), all aspects of the study will be monitored by designated investigators of the sponsor, CDC. For such monitoring purposes, the HIRRC investigators agree to allow access to the clinical supplies, dispensing, storage areas, and the clinical files of the study participants, and, if requested, agree to assist in such monitoring.

In certain circumstances, a secondary audit may be conducted by the sponsor, CDC, or its designee. The HIRRC investigators will be informed if this is to take place and advised as to the nature of the audit.

11.6 Retention of Records

As required by applicable regulations, HIRRC investigators must retain all study records in a secure and safe facility. The HIRRC investigators must consult a representative of the sponsor, CDC, before intended disposal of any study records, and must notify the CDC of any change in the location, disposition, or custody of the study files. The period of record retention should be consistent with the record retention policies of the Dominican Republic, or the Committee for Proprietary Medicinal Products (CPMP) of the European Agency for the Evaluation of Medicinal Products, whichever is longer. The CPMP requires retention for the maximal period of time permitted by the institution, but not less than 15 years. HIRRC shall destroy the Participant Identification Form containing confidential information at the end of any applicable retention periods, or after 15 years, whichever is later. CDC shall retain for 15 years copies of those anonymous records furnished to it by HIRRC for data entry and analysis purposes.

11.7 Use of Information and Publication

The principal parties to and collaborators with the study -- HIRRC, CDC, WHO, PATH, Bioject, and the serology laboratory -- recognize the importance of communicating medical research results and therefore each encourages publication of the results of this study in reputable scientific journals and at seminars or conferences.

All parties agree to furnish the others with a copy of any proposed public presentations or publication related to the study. The comments thereon shall be replied to the submitting party without undue delay, and not later than within 60 days. If comments or suggestions by any of the parties are not accepted, the senior author of the abstract or manuscript and representatives of the other parties shall promptly meet and endeavor to agree mutually on the final wording and disposition of the publication. In the event such agreement is not

HIRRC/CDC Needle-free Intradermal	Page 108	File: 4785-ID-INF-Prot-Engl-2008Jun24.doc
Influenza Study - CDC-ISO-4785	of 138	2008-Jun-24

achieved, the author(s) of any abstract, presentation, or publication shall duly disclose therein the objections of the other party(ies). No participant in this research may be listed as an author or co-author on a publication or conference abstract presentation without their prior consent. The same procedure and policy shall apply to publication or presentation of the results of prematurely discontinued and any other noncompleted aspects of this study.

Due regard shall be given to the legitimate interests of Bioject and any other manufacturer whose products are used in the study. Such interests include technical accuracy, interpretive conclusions, manuscript co-authorship, obtaining patent protection, coordinating and maintaining the proprietary nature of submissions to health authorities, coordinating with other ongoing studies in the same field, and protecting confidential data furnished in furtherance of the study.

Unpublished results from investigations shall not be made available to any outside party not otherwise involved in the study by the investigating team without similar use of the presentations and publications procedure as outlined previously. Neither Bioject nor any other manufacturer whose products are used in the study shall quote from publications by investigators in its scientific information or promotional material without full acknowledgment of the source (i.e., author and reference).

It is intended and understood by the Dominican investigators at HIRRC and the U.S. investigators at CDC that the information generated in this study may be used by the manufacturer(s) of product(s) used therein in connection with the development of its product and therefore may be disclosed to government agencies in various countries. To allow for the use of information derived from the study, within three months after the conclusion of the study and its data analyses, upon request, the HIRRC and CDC investigators will provide such manufacturer(s) with copies or summaries of clinical data and records, except confidential Participant Identification Form information.

No manufacturer furnishing products used in this study may make any claims to the public, in writing or in oral presentations, nor may it cite in its advertising nor product labeling, any statement suggesting or implying that HIRRC, CDC, WHO, or PATH in any way endorse the products. However, a manufacturer may state that it collaborated with these organizations in experimental use of its products. It may cite published results of the study. It may use unpublished results for regulatory or commercial purposes other than publication or advertising.

Specimens of serum, extracts, or isolates provided to laboratories under this protocol shall not be transferred to other parties without an express written *Materials Transfer Agreement* executed by HIRRC and CDC.

11.8 Statement of Obligations

11.8.1 Sponsor and Monitor

The sponsor (CDC) has already, or will:

HIRRC/CDC Needle-free Intradermal	Page 109	File: 4785-ID-INF-Prot-Engl-2008Jun24.doc
Influenza Study - CDC-ISO-4785	of 138	2008-Jun-24

- A. Conduct one or more prestudy visits to:
 - 1. Establish the acceptability of the facility and record this in a written report (memorandum or form).
 - 2. Discuss the proposed trial with the clinical investigators at the HIRRC, supply the case report form, draft protocol, and other documents for review and approval.
 - 3. Discuss with the investigator regulatory requirements with respect to informed consent, IRB or EC approval of the trial, the protocol, including protocol amendments, and informed consent changes.
- B. Conduct periodic site visits to:
 - 1. Assure adherence to the protocol.
 - 2. Review case report forms and medical records for accuracy and completeness of information.
 - 3. Examine pharmacy records for documentation of quantity and date of receipt of investigational supplies, dispensation and accountability data for administration to each Participant, loss of materials, contamination, and unused supplies.
 - 4. Record and report (summarize) observations on the progress of the trial and continued acceptability of the facilities in a site visit report.
 - 5. Review investigator files for required documents, e.g., protocols, protocol amendments, IRB or EC approvals (protocols, amendments, informed consent, etc), IRB charter and membership, and communications to and from the IRB or EC and the investigator.

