10.4.6 Blinding

The study will be observer-blinded. The study investigators, plus the study clinical staff who will assess and record adverse reactions, the laboratory personnel who will process and perform serological assays on the specimens, as well as the participant's parent(s) will all be unaware of the study group into which the participant is assigned. Only the

HIRRC/CDC Needle-free Intradermal	Page 73	File: 4785-ID-INF-Prot-Engl-2008Jun24.doc
Influenza Study - CDC-ISO-4785	of 138	2008-Jun-24

unblinded *injection nurse* and *holding assistant* will observe the method of injection. None of these unblinded staff will be involved in assessing or recording adverse events in the Case Report or other forms. Parents will be required to remain outside the injection room during the 1 to 2 minutes necessary to carry out the vaccination. The *allocation group randomization cards* (see 10.4.4.3) will be destroyed and discarded at the time when the device is filled for the associated participant. No written record of vaccination dose or route will be maintained in the study clinic.

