10.9 Stopping Rules to Suspend Vaccination

10.9.1 Phase I

During phase I (n=48), upon the occurrence of *Serious Adverse Events* in three (3 [6%]) or more enrolled vaccinees, or incidents of *entire-limb swelling*^{Rennels2000} or other *severe local reactions* at the **INF** injection site in five (5 [10%]) or more vaccinees, which, in the opinion of any of the Principal or Senior Dominican or U.S. Investigators are *possibly-related* or *probably-related* to the investigational vaccination (see section 10.5.2.2 for definitions).

Further **INF** vaccination for all participants will be suspended immediately until review of the data by the DSMB. Upon analysis using unblinded access to the study group code allocations, the DSMB shall provide either its clearance to resume vaccination, with restrictions, if any, as appropriate, or its denial to proceed. (The IRBs will be contemporaneously informed of any such suspension, as well as the outcome of the DSMB review, and the investigators will adhere to any resulting IRB guidance.)

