11.8.2 Clinical Investigators

- A. Institutional Review Board or Ethics Committee. The Dominican Principal and Senior Investigators must assure the sponsor or monitor that the IRB or EC of the Fundación Dominicana de Infectología (FDI):
 - 1. Meets regulations as defined in 21 CFR Part 56 of the U.S. Code and other applicable requirements.
 - 2. Has authority delegated by the parent institution, which authority is found in the by-laws of the IRB or EC, its operating guidelines or its charter, to approve or disapprove clinical trials and protocols, including informed consent forms and other documents (protocol amendments, information to be supplied to participants concerning informed consent, etc).
 - 3. Complies with proper personnel makeup of an IRB or EC.
 - 4. Convenes meetings using acceptable rules of order for making decisions, recording such decisions and implementing them.
 - 5. Files contain (a) documentation of its decisions such as are found in IRB or EC minutes and correspondence, (b) written guidelines or bylaws governing IRB or EC functions, (c) protocols, (d) protocol information

HIRRC/CDC Needle-free Intradermal	Page 110	File: 4785-ID-INF-Prot-Engl-2008Jun24.doc
Influenza Study - CDC-ISO-4785	of 138	2008-Jun-24

to be supplied to the subject, (f) correspondence between the IRB or EC and the investigator (consent changes, protocol amendments, etc).

- B. Informed Consent of Human Subjects. The Dominican Principal and Senior Investigators must assure the sponsor or monitor that the informed consent form for participant subjects:
 - 1. Meets regulations as defined in 21 CFR Part 50 of U.S. Code for Informed Consent, and other applicable requirements.
 - 2. Has been approved by the FDI IRB or EC, including, when required, information to be given to the participant regarding the trial he or she is enrolled in.
 - a. Informed consent includes the basic elements and any additional elements necessary.
 - b. The participant and a study site representative sign the form and the participant is given a copy.
- C. Storage and Dispensing of Study Supplies. The Dominican Principal and Senior Investigators (or pharmacist) must demonstrate to the sponsor or monitor that:
 - 1. Adequate and accurate written records show receipt and disposition of all study supplies, including dates, serial or lot numbers, quantities received, and each quantity dispensed, administered, or used, with identification of each participant.

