 - 2. Purpose and reasons are given in written records for study material disposal, e.g., the amount contaminated, broken, or lost, and the quantity returned to the sponsor.
- D. **Case Report Forms**. The Dominican Principal and Senior Investigators must assure the sponsor that:
 - 1. Case Report Forms, when completed, accurately reflect the medical records on each participant.
 - 2. Case report forms and medical records will be accessible to the sponsor or other authorized inspectors during site visits.
- E. **Files and Records**. (See section 11.6.) The Dominican Principal and Senior Investigators must assure the quality, integrity, and content of his or her files that will be inspected by the sponsor, and any other authorized inspectors. The files must contain, as a minimum:
 - 1. Correspondence to and from the IRB or EC and the investigator.
 - 2. Documents that include:
 - a. IRB/EC-approved protocols.
 - b. IRB/EC-approved protocol amendments.

HIRRC/CDC Needle-free Intradermal	Page 111	File: 4785-ID-INF-Prot-Engl-2008Jun24.doc
Influenza Study - CDC-ISO-4785	of 138	2008-Jun-24

- c. IRB/EC-approved informed consent and information supplied to the participant.
- d. IRB/EC charter, membership, and qualifications.
- 3. Clinical supplies:
 - a. Record of receipt, date and quantity, batch or lot number.
 - b. Disposition dates and quantity administered to each participant.
 - c. Inventory records.

12. Questions and Answers on Study Plan, Policies, Ethics

12.1 Why is this study being done in infants from 6 to 24 months of age, rather than first in adults or older children?

There is already a substantial literature documenting the clinical immune response and safety for the intradermal administration of inactivated influenza vaccine to adults (see sections 9.4.2 to 9.4.4), and in some studies to older children^{Beasley1960,} or to children of unspecified age^{Bruyn1947, Sigel1957}. But there is little^{Bruyn1949b,} Klein¹⁹⁶¹ or no data on intradermal influenza vaccination in the age group of infants 6 months to 2 years who are particularly susceptible to serious morbidity and mortality from this disease, and who are now recommended for routine universal vaccination in some developed countries.

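### The accountability rules in 11.2 and 11.8 require per-child quantity and supply records that reveal the arm, which contradicts the blinding in 10.4.6 and 10.6.11

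*Protocol*

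**What the plan says.** **Blinding.** Protocol 10.4.6 lists the people who are to be unaware of group: "The study investigators, plus the study clinical staff who will assess and record adverse reactions", together with laboratory staff and parents. Only the injection nurse and the holding assistant see the method, and "None of these unblinded staff will be involved in assessing or recording adverse events in the Case Report or other forms". The allocation cards are destroyed, and "No written record of vaccination dose or route will be maintained in the study clinic". Section 10.6.11 keeps the codes from the investigators until the clinical work and the serology are complete, apart from the exceptions in 10.4.4.

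**Accountability.**
- 11.2 makes the hospital investigators account for product subject by subject.
- 11.8.2 C.1 makes the Dominican Principal and Senior Investigators (or pharmacist) show the sponsor or monitor written records of all study supplies, covering "quantities received, and each quantity dispensed, administered, or used, with identification of each participant".
- 11.8.2 E.3.b lists among the minimum contents of those investigators' own files: "Disposition dates and quantity administered to each participant".
- 11.8.1 B.3 has the sponsor, at periodic site visits, "Examine pharmacy records for documentation of quantity and date of receipt of investigational supplies, dispensation and accountability data for administration to each Participant".
- 11.5 states that "all aspects of the study will be monitored by designated investigators of the sponsor, CDC", and 10.7.2 places monitoring visits both during and after the study.

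**Relatedness.** Under 10.5.2.2.4 the investigator decides the relationship to vaccine. Under 10.9.1, an event counts toward suspension if it is related "in the opinion of any of the Principal or Senior Dominican or U.S. Investigators".

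**The concern.** Accountability wording of this kind is harmless when every arm receives the same volume from the same device. Here the arms differ in exactly those two things, so a per-child record of quantity and supplies is an allocation list under another name. Section 11 puts that list in the files of the Dominican Principal and Senior Investigators and has CDC inspect accountability data while the trial is running. No passage masks the records, restricts them to unblinded staff or postpones inspection until the code is released.

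What is at stake is the safety assessment. The investigators who would hold the records also decide whether a serious event, a severe local reaction or a high fever was possibly or probably related. Those decisions determine what is counted under 10.9 and on two lines of the 10.10 gate. The protocol guards against much smaller leaks. Section 10.4.6.3 keeps the nurses' notes of a blood drop or wetness away from the physicians, and 10.6.8 has the nurse do the early site check in case skin dimpling gives the device away.

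**Working it through.** The plan gives no figure to reproduce. The check sets the passages against each other, then counts how much the records reveal.

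**1. What must be recorded per child.** C.1 asks for each quantity used, over all study supplies, identified by participant. E.3.b asks for the quantity given to each participant. Section 11.2 asks for subject-level accounting without naming the volume per child. B.3 names accountability data for administration to each child, also without the word volume. The explicit demand for per-child quantity therefore comes from C.1 and E.3.b; 11.2 and B.3 supply the general duty and the inspection.

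**2. What the record reveals.** Inputs from 10.1.1, 10.1.2, 10.4.1 and 10.4.2.3:

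| Arm | Children | Volume per dose | Device supplies |
|---|---|---|---|
| IM-NS-0.25 (control) | 150 | 0.25 mL | needle and syringe |
| IM-NS-0.1 | 150 | 0.1 mL | needle and syringe |
| ID-JI-0.1 | 150 | 0.1 mL | jet cartridge and spacer |

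- Volume alone: all 150 controls are identified. The other 150 + 150 = 300 children are known to be in a reduced-dose arm, with a 1 in 2 guess between the two. Expected correct identification = (150 + 300 × 1/2) / 450 = 300/450 = 66.7%, against 1/3 = 33.3% by chance.
- Phase I only (16 per arm): (16 + 32 × 1/2) / 48 = 32/48 = 66.7%.
- Volume plus supply item: 450/450 = 100%.
- Third visit (10.4.1): a mock injection for controls against 0.25 mL for the other arms separates the controls again, though only from day 56.

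**3. Which decisions depend on relatedness.**
- 10.9, phase I: related serious events in 3 of 48 children, or related entire-limb swelling or severe local reactions in 5 of 48. Phase II: 16 and 20 of 402. All four counts need a relatedness judgement.
- 10.10: the serious-event line (excess of 3 or more over control) and the fever line (excess of 4 or more) need one. Limb swelling, induration, erythema and pain do not. That is 2 of 6 lines.
- Near a threshold one judgement matters. On the serious-event line, 3 − 0 = 3 drops the arm, whereas 2 − 0 = 2 or 3 − 1 = 2 lets it continue.

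**4. Can both sets of rules be met?** Under 10.4.6 the clinic keeps no record of dose or route and the investigators do not know the group. Under E.3.b the investigators' files must hold each child's quantity. Completing those files after code release would satisfy both, but the protocol does not say so, and B.3 has per-participant accountability data examined at periodic visits.

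**The case against.** The strongest reply is that the trial-specific procedures follow 10.4.6, not section 11. The cards are destroyed (10.4.4.4, 10.6.8). The confirmation sticker shows only study number and dose letter (10.4.4.3). The injection steps have the nurse record observations, lot number and clock time, not volume or device (10.4.2.3). All arms are filled from the same vial (10.4.2.2), so vial dispensing reveals nothing. The associated documents in section 13 include no accountability form. A site working from section 10 would create no revealing log. That stands, and it means the documents show a contradiction, not an unblinding that will occur.

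Other points that stand in whole or in part:
- C.1 allows a pharmacist to hold the records and B.3 speaks of pharmacy records. The relief is limited: the staff list in 10.6.2 has no pharmacist, and E.3.b concerns the investigators' own files.
- C.1 and E.3.b set no date, and monitoring also runs after the study. Only the periodic visits in B.3 point to inspection during the trial.
- Section 11.5 says designated CDC investigators. They need not be the Principal or Senior Investigators who judge relatedness. The route through the Dominican files does not depend on this.
- The 10.9 counts are pooled over arms, any one of the named investigators can call an event related, and suspension leads to unblinded review by the safety board. One biased downgrade therefore need not suppress a trigger. A biased upgrade could still add to a count, and the 10.10 gate is a comparison between arms.

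A reader might infer that the observer blinding is untrue as stated, or that the whole trial result is compromised. The documents support neither. The first assumes that section 11 overrides 10.4.6, which nothing says. The second overlooks that the antibody assays are done by blinded laboratory staff.

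**Conclusion.** The contradiction is real. Sections 11.2, 11.8.1 B.3 and 11.8.2 C.1 and E.3.b, taken together and followed as written, defeat 10.4.6 and the withholding of codes in 10.6.11. The records would identify 150 of 450 children by volume alone, and all 450 by volume plus supply item. The exposure is confined to safety judgements that rest on relatedness: what counts under 10.9, and the serious-event and fever lines of 10.10. That gate concerns only the 48 phase I children.

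The conclusion assumes that quantity is logged as volume, as the text asks, and that the files are completed before code release, which the text neither requires nor rules out. If staff logged only that a dose was given, the arm would not show, but that would depart from C.1 and E.3.b. The size of any bias cannot be derived from the documents. The passages should be reconciled.

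**What to change.** Amend 11.2, 11.8.1 B.3 and 11.8.2 C.1 and E.3.b together. Until the code is released, records held by the investigators or inspected by CDC monitors show per child only the date, the lot or vial number and *dose given*, plus an aggregate reconciliation of volume and devices. The aggregate should span many children rather than one clinic day, since 10.6.2.2 starts recruitment at two children a day.

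Any per-child volume or device record is completed only by the unblinded injection nurse, sealed, and sent to the independent party or the safety board. It is reconciled after code release, or earlier by the safety board for cause. The sentence in 10.4.6 that bars written dose or route records must be amended to permit this sealed record; otherwise the fix creates a new contradiction.

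The cost is wording in four accountability items and one blinding sentence, and one sealed form completed by existing staff. The downside is that accountability for each child is verified later than at each site visit. No dose, schedule or stopping rule changes.

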11.8.2 Clinical Investigators

- A. Institutional Review Board or Ethics Committee. The Dominican Principal and Senior Investigators must assure the sponsor or monitor that the IRB or EC of the Fundación Dominicana de Infectología (FDI):
 - 1. Meets regulations as defined in 21 CFR Part 56 of the U.S. Code and other applicable requirements.
 - 2. Has authority delegated by the parent institution, which authority is found in the by-laws of the IRB or EC, its operating guidelines or its charter, to approve or disapprove clinical trials and protocols, including informed consent forms and other documents (protocol amendments, information to be supplied to participants concerning informed consent, etc).
 - 3. Complies with proper personnel makeup of an IRB or EC.
 - 4. Convenes meetings using acceptable rules of order for making decisions, recording such decisions and implementing them.
 - 5. Files contain (a) documentation of its decisions such as are found in IRB or EC minutes and correspondence, (b) written guidelines or bylaws governing IRB or EC functions, (c) protocols, (d) protocol information

HIRRC/CDC Needle-free Intradermal	Page 110	File: 4785-ID-INF-Prot-Engl-2008Jun24.doc
Influenza Study - CDC-ISO-4785	of 138	2008-Jun-24

to be supplied to the subject, (f) correspondence between the IRB or EC and the investigator (consent changes, protocol amendments, etc).

- B. Informed Consent of Human Subjects. The Dominican Principal and Senior Investigators must assure the sponsor or monitor that the informed consent form for participant subjects:
 - 1. Meets regulations as defined in 21 CFR Part 50 of U.S. Code for Informed Consent, and other applicable requirements.
 - 2. Has been approved by the FDI IRB or EC, including, when required, information to be given to the participant regarding the trial he or she is enrolled in.
 - a. Informed consent includes the basic elements and any additional elements necessary.
 - b. The participant and a study site representative sign the form and the participant is given a copy.
- C. Storage and Dispensing of Study Supplies. The Dominican Principal and Senior Investigators (or pharmacist) must demonstrate to the sponsor or monitor that:
 - 1. Adequate and accurate written records show receipt and disposition of all study supplies, including dates, serial or lot numbers, quantities received, and each quantity dispensed, administered, or used, with identification of each participant.
 - 2. Purpose and reasons are given in written records for study material disposal, e.g., the amount contaminated, broken, or lost, and the quantity returned to the sponsor.
- D. **Case Report Forms**. The Dominican Principal and Senior Investigators must assure the sponsor that:
 - 1. Case Report Forms, when completed, accurately reflect the medical records on each participant.
 - 2. Case report forms and medical records will be accessible to the sponsor or other authorized inspectors during site visits.
- E. **Files and Records**. (See section 11.6.) The Dominican Principal and Senior Investigators must assure the quality, integrity, and content of his or her files that will be inspected by the sponsor, and any other authorized inspectors. The files must contain, as a minimum:
 - 1. Correspondence to and from the IRB or EC and the investigator.
 - 2. Documents that include:
 - a. IRB/EC-approved protocols.
 - b. IRB/EC-approved protocol amendments.

HIRRC/CDC Needle-free Intradermal	Page 111	File: 4785-ID-INF-Prot-Engl-2008Jun24.doc
Influenza Study - CDC-ISO-4785	of 138	2008-Jun-24

- c. IRB/EC-approved informed consent and information supplied to the participant.
- d. IRB/EC charter, membership, and qualifications.
- 3. Clinical supplies:
 - a. Record of receipt, date and quantity, batch or lot number.
 - b. Disposition dates and quantity administered to each participant.
 - c. Inventory records.

12. Questions and Answers on Study Plan, Policies, Ethics

12.1 Why is this study being done in infants from 6 to 24 months of age, rather than first in adults or older children?

There is already a substantial literature documenting the clinical immune response and safety for the intradermal administration of inactivated influenza vaccine to adults (see sections 9.4.2 to 9.4.4), and in some studies to older children^{Beasley1960,} or to children of unspecified age^{Bruyn1947, Sigel1957}. But there is little^{Bruyn1949b,} Klein¹⁹⁶¹ or no data on intradermal influenza vaccination in the age group of infants 6 months to 2 years who are particularly susceptible to serious morbidity and mortality from this disease, and who are now recommended for routine universal vaccination in some developed countries.

The investigational spacer to be studied in this trial has already been subjected to a number of well-conducted studies on adults without serious adverse consequences (see section 10.4.3.6). Thus, it is reasonable now to study young children in order to gather essential data for policymaking on how such participants may be protected in the event of pandemic. This study is phased with conservative stopping rules that can quickly respond to any clinical outcomes suggesting untoward risks to these children.

12.2 Why is this study being done in the Dominican Republic and not in the United States or Europe, where its sponsor and principal parties are based?

This kind of study could and should very well be conducted in the U.S. or Europe, as the questions it poses are relevant to those geographic areas as well. However, the collaboration supporting this study benefits from the technical scientific and/or financial contributions of WHO and PATH, organizations with primary missions to seek answers to the health problems of the developing world. This global perspective is also within the mission of CDC, which recognizes that national health and security depends on the health and security of all nations. The selection of the HIRRC as a partner in this study resulted from its excellent track record of clinical trials of vaccines and antimicrobials (see section 10.2.1).

HIRRC/CDC Needle-free Intradermal	Page 112	File: 4785-ID-INF-Prot-Engl-2008Jun24.doc
Influenza Study - CDC-ISO-4785	of 138	2008-Jun-24

12.3 Why is the study planning to use Vaxigrip[®] instead of an influenza vaccine licensed in the U.S.A.?

The brand of influenza vaccine to use in this study was selected by a process of elimination from among the seven major products on the international market, of which three are now sold in the U.S.

One priority was to minimize the number of "investigational" aspects of the study by using an influenza vaccine already licensed and marketed in the Dominican Republic. There are three: (1) **Vaxigrip** (in prefilled syringes), (2) **Fluarix**[®] (GSK, manufactured in Dresden, Germany), and (3) **Agrippal**[®] **S1** (Chiron, manufactured in Siena, Italy). Well after planning for the study began, **Fluarix** was licensed in the U.S., but worldwide it is only available in prefilled glass syringes of 0.5 mL. Thus, using **Fluarix** would be wasteful for administering the 0.25 mL and 0.1 mL doses for the two needle-syringe study arms. Also, it would be impractical to transfer 0.1 mL from the glass **Fluarix** syringe into the male tip of the Biojector cartridge, requiring an expensive, disposable Luer adapter (and would still waste 80 percent of the vaccine left in the syringe). **Agrippal S1** is not licensed in the U.S., and its prefilled syringes would produce the same obstacles as **Fluarix**. **Agrippal S1** also comes in single-dose vials without preservative, which means they cannot be used to fill multiple syringes.

Neither (4) **Fluzone**[®] (Sanofi-Pasteur, manufactured in Swiftwater, PA), (5) **Fluvirin**[®] (Chiron, manufactured in Liverpool, UK), (6) **BegrivacTM** (Chiron, manufactured in Marburg, Germany), nor (7) **Fluad**[®] (Chiron, manufactured in Siena, Italy) are licensed for use in the Dominican Republic. Moreover, **Fluvirin** is not licensed for use in ages under 4 years. **Begrivac** and **Fluad** are also adjuvanted products, which may increase reactogenicity when administered into the skin.

12.4 Why is the study not being carried out under Investigational New Drug (IND) application to the FDA/CBER because of the non-labeled ID route and reduced dosage?

The original intention for this study was to seek such regulatory oversight by FDA, as an indicator of the most rigorous standards of research quality, even though it is not technically required for studies outside the U.S. for vaccines not anticipated to seek U.S. licensure. However, consultations with [name] ([contact]) of the Center for Biologics Evaluation and Research of FDA indicated that the agency would be unable to accept such a filing. This is because FDA has no documentation on file for the *chemistry, manufacturing, and controls* ("CMC") of Vaxigrip. Such information is very extensive and expensive to assemble, and is proprietary to the manufacturer. In the absence of any plans to bring this product into the U.S. market, Sanofi-Pasteur would not do so for this study.

HIRRC/CDC Needle-free Intradermal	Page 113	File: 4785-ID-INF-Prot-Engl-2008Jun24.doc
Influenza Study - CDC-ISO-4785	of 138	2008-Jun-24

The planned importation of multidose vials of Vaxigrip into the Dominican Republic for investigational use in this study will require the authorization of the national pharmaceutical regulatory authority of the Dominican Republic, the Dirección General de Drogas y Farmacias of the SESPAS [Ministry of Health]. In addition, such studies in its facilities must be approved by appropriate officials. Thus, SESPAS has both regulatory oversight and political authority over this study, and will be exercising it accordingly.

Before implementation, this study will undergo and require consideration and approval not only from the IRBs of CDC and the FDI, but also from appropriate review bodies of the Dominican Republic Ministry of Health (SESPAS), the World Health Organization (WHO), and the Program for Appropriate Technology in Health (PATH). Such reviews will inevitably apply rigorous ethical, scientific, and policy scrutiny that will more than compensate for the absence of FDA oversight via the IND process.

12.5 How will one know the amount of vaccine actually delivered into the skin by the intradermal spacer, versus going into deeper tissues, or dripping out onto the skin?

It is very difficult for any vaccination study to document the amount of vaccine that actually enters the intended target tissue, whether skin (ID), muscle (IM), or fat (SC). Indeed, there is evidence that a substantial proportion of intended IM injections likely end up in the fat. Health workers have been found to underestimate the fat pad thickness in selecting needle length, or do not insert enough of it.^{Cockshott1982, Poland1997}

Proving the site of deposition or measuring the quantity of antigen reaching various tissue compartments would require contrast-imaging, biopsy, and similar expensive and invasive procedures. Regulatory agencies consider these unnecessary in most routine clinical trials because noninvasive measures and outcomes are available to document that the vaccine achieves its purpose. For ID injections, the presence of a wheal immediately after injection, and the absence of clear liquid drops on the skin, suggest that the dose went neither too deep nor too shallow. Both these variables will be collected in this study by observation immediately after vaccine doses 1 and 2 and noted on the Case Report Form.

In general for almost all vaccine trials, the immune response is empirical evidence of success. If antigen is placed into the wrong compartment in some participants, or partly escapes through the injection site, this would be an academic issue if participants are otherwise adequately protected from disease. If not, the immediate observations of the injection site may provide clues to any failure to effectively immunize, and provide a basis for further studies to elucidate the problem, if warranted.

HIRRC/CDC Needle-free Intradermal	Page 114	File: 4785-ID-INF-Prot-Engl-2008Jun24.doc
Influenza Study - CDC-ISO-4785	of 138	2008-Jun-24

12.6 Will the local side effects of intradermal injection be more painful for participants than needle-syringe?

The first studies of the Biojector with intradermal spacer were conducted by anesthesiologist professor Elemer Zsigmond at the University of Illinois (see 0), and suggested that ID injection was less painful than using a needle to administer lidocaine.^{Zsigmond1999a, Zsigmond1999b} Other clinical studies have demonstrated favorable safety and tolerability.

Subjects in a Navy vaccine trial who received Biojector ID injections in one arm and Biojector IM in the other (see 10.4.3.6.2), reported overwhelming preference (26 vs. 3) for either Biojector route over their prior experience with needle-syringe (but no control needle injections were tested).

In a study of infants like this one, it is difficult to assess pain. However, parents and staff will be assessing local pain daily on the diary form and followup visit, by the participant's reaction when the limb is touched or moved.

12.7 Why is there no study arm of children receiving the reduced vaccine dose intradermally using needle-syringe?

Although it would be of intellectual interest to compared two different methods of intradermal delivery -- needle-syringe (N-S) and jet injector (JI) -- such a comparison was precluded for two reasons.

First, adding another study arm would increase the cost of the trial by about onethird, and would extend its duration by that same degree. Resources are insufficient to do so, and delaying the results is deemed inadvisable because of its potential importance for pandemic response. Second, the Mantoux method of needle-syringe injection into the skin is considered impractical for widespread use for reasons of speed, logistics, occupational injuries, and waste disposal burdens (see section 9.1). Thus the data would not be actionable.

12.8 Why was the Biojector system picked for use in this study, rather than other simpler, more economical jet injectors?

It is quite true that there are other needle-free jet injectors on the market or in development that are less complex in their construction than the Biojector, cost less to purchase and to buy their disposable cartridges, do not require CO_2 canisters which can be hard to procure in developing countries, and other reasons that might make them more suitable for use in developing countries than the Biojector.

Despite these disadvantages, however, the Biojector is the only one among them for which substantial data has been accumulated in bench, animal, and clinical

HIRRC/CDC Needle-free Intradermal	Page 115	File: 4785-ID-INF-Prot-Engl-2008Jun24.doc
Influenza Study - CDC-ISO-4785	of 138	2008-Jun-24

